15.1. BACKGROUND LIPID MODIFYING THERAPY

Baseline background lipid modifying therapy is defined as any lipid modifying agents that are on-going at the time of randomization. It will be presented by treatment group in separate table and listing by category, ATC class 4 and coded medication name.

15.2. ADDITIONAL POST-RANDOMIZATION ADJUNCTIVE TRIGLYCERIDE-LOWERING THERAPY

The number and percent of patients requiring additional (post-randomization) TG-lowering therapy (only when TG>1000) will be summarized by treatment group, ATC class 4 and medication name, as well as provided in a listing. The TG lowering medication will be identified as post-randomization concomitant medications with indication of 'hypertriglyceridemia'.

15.3. ADDITIONAL POST-RANDOMIZATION LIPID MODIFYING THERAPY

The number and percent of patients in each treatment group requiring additional (post-randomization) lipid-lowering therapy will be summarized by treatment group, ATC class 4 and medication name as well as provided in a listing. The lipid-lowering therapy includes all post-randomization concomitant medications based on ATC class 2 = lipid-modifying agent.

16. STUDY MEDICATION COMPLIANCE AND EXPOSURE

Compliance to study medication will be presented for the SAF. At visit Week -1 (S3) and each patient visit during the study, clinical site staff will count the number of tablets that are returned as unused and query the patient with regards to daily intake.

16.1. DERIVATIONS

Compliance with placebo-run in (as an overall group) and double-blind study medication by treatment group, based on the drug accountability data, will be calculated as the number of tablets taken (total dispensed – total returned) divided by the number of days on treatment within each of the 2 periods.

During the run-in period, the compliance will be summarized as a single overall group and during the double-blind period, compliance will be summarized by treatment group (bempedoic acid and placebo).

Compliance will not be computed by visit.

A 35-day supply of single-blind placebo drug will be dispensed one time at Week -4 (Visit S2) for the 4-week placebo run-in period of the study. Double-blind IMP will be dispensed in 100 day supply increments to patients by appropriate clinical site personnel. Patients will receive one 100-day supply bottle at Week 0 (Visit T1), Week 12 (Visit T4), and two 100-day supply bottles at Week 24 (Visit T5).

The treatment is taken once daily and it is assumed that the patient takes medication on the visit day at which their medication is initially dispensed to the day of their last medication return date. For example, if the initial dispense date is Day 1 and the last return date is Day 84, then the patient should have taken the first tablet at Day 1, once a day on Days 2 to 83 and 1 tablet on Day 84; hence, the total number of prescribed tablets would be 84.

For subjects who did not return any bottle during the run-in or double-blind period, their compliance will be set to missing.

Treatment exposure will be calculated in weeks as (date of last dose of study medication – first date of first dose of study medication +1)/7. Descriptive statistics will be presented for exposure as well as categorization into time periods. (e.g., <12weeks, 12-<24 weeks, 24-<48 weeks and >=48 weeks, etc.).

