8. TREATMENT OF PATIENTS

8.1. Description of IMP

Table 4: Investigational Medicinal Products

Product Name:	Investigational Medicinal Product	
	Bempedoic acid	Placebo
Dosage Form:	██████████ tablets	██████████ tablets
Unit Dose:	180 mg	Not applicable
Container/Closure ^a	100-count bottle (depending upon visit) with screw on, childproof cap	35- and/or 100-count bottle with screw on, childproof cap
Route of Administration:	Oral, daily, with or without food	Oral, daily, with or without food
Physical Description:	██████████	██████████

^a A 100-day supply of IMP will be included in the 100-count bottle and a 35-day supply of single blind placebo lead-in will be included in the 35-count bottle.

Please see Pharmacy Manual for detailed storage requirements and instructions.

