9. INVESTIGATIONAL MEDICINAL PRODUCT

9.1. Investigational Medicinal Product Supply and Control

The Sponsor will supply the IMP for this study. The IMP for this study includes bempedoic acid (180-mg [REDACTED] tablets) and matching placebo ([REDACTED] tablets). IMP will be distributed and released in accordance with regional and local requirements during the conduct of the study.

The MED ID number (an identifier on the study drug packaging) will be obtained via IWRS and used to select placebo for the single-blind placebo run-in period and double-blind IMP for the treatment period from available clinical supplies at the clinical site.

A 35-day supply of single-blind placebo drug will be dispensed one time at Week -4 (Visit S2) for the 4-week placebo run-in period of the study. Double-blind IMP will be dispensed in 100-day supply increments to patients by appropriate clinical site personnel. Patients will receive one 100-day supply bottle at Week 0 (Visit T1), Week 12 (Visit T4), and two 100-day supply bottles at Week 24 (Visit T5). At Week 12, patients will return their first bottle and tablets will be counted by study personnel who will then dispense a second bottle. At Week 24, tablets from the second bottle will be counted and the final 2 bottles dispensed. At Week 52, tablets will be counted by study personnel from the 2 bottles dispensed at Week 24.

Please see Pharmacy Manual for detailed storage requirements and management instructions.

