10.2.7. Treatment Week 12 (Visit T4; 85 ±3 days)

If the patient is withdrawing early from the study at this visit, proceed to [Section 10.3.2](#) for the list of the required assessments.

If the patient is withdrawing from IMP treatment at this visit, proceed to [Section 10.2.10](#) for the list of the required assessments. The patient will be asked to continue to be followed for safety using the protocol-specified visit schedule. If the patient consents for follow-up, schedule the next protocol-specified visit.

Patients who do not provide consent to continue to return to the clinic for safety assessments after withdrawing from IMP treatment will be asked to participate in phone calls from the site at protocol-specified visits, or at a minimum at 52 weeks, to inquire about the patient's current health status and collect information on AEs (eg, recent procedures, hospitalizations, and if the patient has died, the cause of death). If the patient consents for telephone contacts, schedule the next protocol-specified visit.

Patients will undergo the following assessments and procedures at Week 12 (Visit T4):

- Concomitant and prohibited medication review (ongoing)
- Assess AEs, SAEs, and potential clinical endpoints since last visit (ongoing)
- Weight
- Vital signs

- Clinical laboratory evaluations:
 - Hematology, blood chemistry, and urinalysis
 - Basic fasting lipids (TC, calculated LDL-C, HDL-C, non-HDL-C, and TG)
 - apoB
 - HbA_{1C}
 - hs-CRP
- Conduct diet and exercise counseling
- Return of IMP; assessment and recording of IMP compliance
- IWRS contact to obtain the MED ID number for IMP
- Dispense IMP and provide dosing instructions (one 100-day supply bottle)
- Schedule next visit

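### SAP 16.1 counts unreturned tablets as taken but ends the day count at the last return, so a patient lost after Week 12 scores about 216% compliant

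*SAP*

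**What the plan says.** SAP 16.1 sets out the calculation in four steps.

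- **Numerator and denominator.** Compliance is the "number of tablets taken (total dispensed – total returned) divided by the number of days on treatment", taken separately for the run-in and the double-blind period.
- **Day count.** The patient is assumed to dose from the first dispensing visit "to the day of their last medication return date". In the worked example, dispensing is on Day 1 and the last return on Day 84, so "the total number of prescribed tablets would be 84".
- **Only rule for unreturned drug.** "For subjects who did not return any bottle during the run-in or double-blind period, their compliance will be set to missing".
- **Supply.** "Patients will receive one 100-day supply bottle at Week 0 (Visit T1), Week 12 (Visit T4), and two 100-day supply bottles at Week 24".

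Protocol 8.1 (footnote to Table 4) gives the bottle size: "A 100-day supply of IMP will be included in the 100-count bottle". Protocol 9.1 puts the return of one bottle and the issue of the next at the same visit: "At Week 12, patients will return their first bottle and tablets will be counted by study personnel who will then dispense a second bottle". Compliance is presented for the Safety Analysis Set. It is also on the DMC output list (SAP Appendix 3, Table 14.1.5.1), with no separate derivation for interim cuts.

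**The concern.** Numerator and denominator cover different periods once a bottle stays out. A new bottle adds its full count to the numerator on the day it is dispensed. It adds days to the denominator only if something is returned later. A patient who disappears after collecting a bottle is therefore credited with every tablet in it, taken over no additional days. The missing-data rule does not catch this patient, because an earlier bottle did come back, and the SAP sets no cap.

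The result is an impossible value for a patient whose adherence after that visit is unknown. The figures concerned are those a reader or the DMC would use to judge how well study drug was taken.

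**Working it through.** **Inputs**
- 100 tablets per bottle, one tablet daily (Protocol 8.1, SAP 16.1).
- One bottle at Week 0, one at Week 12, two at Week 24 (SAP 16.1, Protocol 9.1).
- Week 12 visit on Day 85 ± 3 (Protocol 10.2.7); Week 24 visit on Day 168 ± 7 (Protocol 10.2.8).
- The visit-day dose is delayed until procedures are finished (Protocol 9.2), so a fully adherent patient has used 84 tablets from bottle 1 by the Day 85 count and returns 100 − 84 = 16.

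**The SAP's own example.** Days = last return day − first dispensing day + 1 = 84 − 1 + 1 = 84. This reproduces the stated 84, so the day count does run to the return date.

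**Formula.** Compliance = 100 × (dispensed − returned) / days to last return.

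**Patient lost after collecting bottle 2 at Week 12 (200 dispensed)**

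| Case | Calculation | Result |
|---|---|---|
| Fully adherent to Day 85, visit-day dose delayed | (200 − 16)/85 | 216.5% |
| Fully adherent, Day 85 dose taken from bottle 1 | (200 − 15)/85 | 217.6% |
| Fully adherent, visit on Day 82, that day's dose from bottle 1 | (200 − 18)/82 | 222.0% |
| Fully adherent, visit on Day 88, dose delayed | (200 − 13)/88 | 212.5% |
| 80% adherent to Day 85 | (200 − 32)/85 | 197.6% |
| No tablet ever taken, bottle 1 returned full | (200 − 100)/85 | 117.6% |

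**Patient lost after Week 24.** Dispensed 100 + 100 + 200 = 400; used by the Day 168 count 167; returned 200 − 167 = 33. Compliance = (400 − 33)/168 = 218.5%.

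**DMC cut.** An adherent patient still on treatment between Weeks 12 and 24 has the same recorded inputs (200 dispensed, 16 returned, last return Day 85) and also scores 216.5%. Between Weeks 24 and 52 the figure is 218.5%.

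**If the day count ended at the last dose instead.** With 184 tablets counted as taken, a last dose on Day 113 gives 184/113 = 162.8%, and on Day 141 gives 184/141 = 130.5%. The value falls to 100% only at Day 184.

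**Opposite error.** A patient who takes every dose to Day 40, stops, and returns 60 tablets on Day 85 scores 40/85 = 47.1%, because days after the last dose stay in the denominator.

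**Arm mean.** Assume the other patients average 97% (not in the documents). Per 1% of patients affected, the shift is 0.01 × (216.5 − 97) = 1.2 points, or 0.01 × (197.6 − 97) = 1.0 point if they were 80% adherent. The share affected is unknown. At 1%, 5% and 10% the first figure gives about 1.2, 6.0 and 12.0 points. Per 1% of patients like the Day 40 example, the shift is 0.01 × (47.1 − 97) = −0.5 points.

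**The case against.** The best case for the plan has four parts.

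1. **The wording leaves room.** The days on treatment are not formally defined, and exposure in the same section runs to the last dose. The missing-data sentence could also be read as applying to anyone who failed to return at least one bottle. Neither reading settles the matter. The Day 84 example points to the return date, and ending at the last dose still leaves the unreturned tablets in the numerator. The natural sense of the missing-data sentence is that nothing came back; if the other sense is meant, it has to be written down.

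2. **The case may be uncommon.** Patients must bring back packaging and unused drug at each clinic visit (Protocol 9.2), drug return is among the end-of-study procedures used at early withdrawal (10.2.10, 10.3.2), and sites must pursue patients lost to follow-up (10.3.1). This stands as an argument about frequency. It does not change the value when the case occurs, and it does not apply at a DMC cut, where the outstanding bottles are simply not yet due. Nor is every unreturned bottle extreme: a completer who fails only to return the Week 12 bottle, with about 17 tablets left, is overstated by about 17/365, or 5 points.

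3. **Nothing inferential depends on it.** This stands in full. SAP Section 5 defines only safety, full and PK sets. The imputation rule (17.1.3) and the on-treatment analysis (17.2.3.3) use the last dose date. Poor adherence after randomization does not remove a patient (Protocol 8.3). The output conventions show median, quartiles and maximum, so a value of 216% would be visible and the median largely unaffected.

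4. **Stronger conclusions do not follow.** A reader might infer that the formula inflates the arm with more loss. The documents do not support that, because late return after stopping works in the opposite direction and the mix is not known. A reader might also infer that compliance is wrong for poorly adherent patients in general. It is not: a patient who misses doses but returns each bottle on schedule is scored correctly.

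**Conclusion.** Followed as written, the rule gives an impossible value in a foreseeable situation, and no other section repairs it. The single-patient result is firm: about 216% for loss after Week 12 given full adherence to Day 85, the visit-day dose taken after the visit, and bottle 2 never returned. The other fully adherent Week 12 cases give 212% to 222%, 80% adherence gives about 198%, and loss after Week 24 about 218%.

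The DMC consequence rests on a literal reading, since no interim derivation is given. The arm-level size is conditional: about 1.2 points in the mean per 1% of patients affected, on an assumed 97% elsewhere, with the share and the net direction both unknown. A fixed shift of, say, 6 points needs an assumed 5% affected and should not be presented as a finding.

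This is a minor point about a descriptive table. It gives no reason to doubt the efficacy analyses.

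**What to change.** Replace the derivation in SAP 16.1 with one based on dispensing intervals: Weeks 0–12, 12–24 and 24–52. The last is treated as a single interval because its two bottles are dispensed together and cannot be separated in time.

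- Include an interval only if every bottle dispensed in it was returned. Otherwise drop both its tablets and its days.
- Set a patient with no complete interval to missing.
- State which interval the visit-day dose belongs to. The example patient then scores 84/85 = 98.8%, or 84/84 = 100% if the Day 85 dose is assigned to bottle 2.
- State that the Week 4 count, after which the same bottle is handed back (Protocol 10.2.5), does not close an interval.
- Report by arm the number of patients with unreturned bottles, and at DMC cuts separate bottles not yet due from bottles overdue.

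Optionally, add a supplementary figure with the day count ending at the recorded last dose, for patients who stopped before returning the bottle. That is a choice of definition rather than a correction, because it makes early stoppers look close to fully compliant.

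The cost is a short SAP text change and a little programming, with no new data. The downside is that some intervals become missing, probably not at random, which is why the counts by arm are needed. The SAP Addendum says the planned analyses are complete, so the practical form now is a corrected table or a footnote in the report.

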17. EFFICACY OUTCOMES

17.1. PRIMARY EFFICACY

17.1.1. PRIMARY EFFICACY VARIABLE & DERIVATION

The primary efficacy endpoint is the percent change from baseline to Week 12 in LDL-C. Baseline LDL-C is defined as the mean of the LDL-C values from Week -1 (Visit S3) and predose Day 1/Week 0 (Visit T1) (last two non-missing values on or prior to Day 1).

In cases where triglycerides (TG) is >400 mg/dL or LDL-C is ≤50 mg/dL, a measured LDL (LDL-M) will be used instead of LDL-C for the analysis of that time point. If both values are available, the LDL-M will be used.

17.1.2. PRIMARY ANALYSIS OF PRIMARY EFFICACY VARIABLE

The null hypothesis, H_0 , will be that there is no difference between bempedoic acid 180 mg/day and placebo in mean percent change from baseline to Week 12 in LDL-C. The alternative hypothesis, H_1 , will be that bempedoic acid 180 mg/day is different from placebo:

$$H_0: \mu_p = \mu_b$$

$$H_1: \mu_p \neq \mu_b$$

where μ_p and μ_b denote the mean percent change from baseline to Week 12 in LDL-C on placebo and bempedoic acid 180 mg/day respectively.

The primary efficacy endpoint will be analyzed using analysis of covariance (ANCOVA), with treatment group and randomization stratification factors (CV risk and baseline statin intensity) as factors and baseline LDL-C as a covariate. In case the of number of subjects within a stratum is too small for a meaningful analysis, the strata may be combined to obtain larger cell size. The ANCOVA will be performed using the FAS, with patients included in their randomized treatment group regardless of the treatment they actually received. To account for the likelihood of unequal variances between the treatment groups, the ANCOVA model will be implemented within mixed model framework and the <repeated/group=> option will be used to allow estimating the residual variances separately between the groups. Assumptions for ANCOVA model will be assessed and if the assumptions are severely violated, a non-parametric rank based method will be performed.

In addition, descriptive statistics will be presented for LDL-C at each visit and for change/percent change from baseline by treatment group for overall population and for each stratification factor.

17.1.3. MISSING DATA METHODS FOR PRIMARY EFFICACY VARIABLE

For the primary endpoint of percent change from baseline to Week 12 in LDL-C values, a pattern mixture model (PMM) will be used to specify different imputation strategies depending on whether the patient is still on study treatment. Patients with missing lipid data at Week 12 who are no longer taking study treatment (defined by date of last dose of study medication is < Week 12 visit date -7) can be assumed to no longer be benefitting from study medication, and their missing value(s) can be assumed to be similar to those in placebo group who remained on study and have data. To account for uncertainty, missing values will be imputed using multiple imputation via a regression based model including stratification and baseline data from placebo subjects only. In this imputation model, treatment group will not be included as a factor.

Patients with missing lipid data at Week 12 who are still taking study treatment (date of last dose of study medication is ≥ Week 12 visit date -7) can be assumed to continue to benefit from study medication, and their missing value(s) can be assumed to be similar to those who remain on study treatment and have data and as a result, lipid values will be imputed based on the observed values in their randomized treatment group at Week 12. To account for uncertainty, missing values will be imputed using multiple imputation via a regression based model including treatment, stratification and baseline data.

Imputed datasets will be analyzed using an ANCOVA model with treatment, CV risk, baseline statin intensity as a factors and baseline LDL-C as a covariate. Approximately 200 imputed datasets will be created, with results from the analysis of each imputed dataset combined using Rubin’s method. The least squares mean (LSM) and standard error (SE) will be provided for both treatment groups, along with the placebo-corrected LSM, its 95% confidence interval (CI) and associated p-value. To account for possibility of unequal variances between the groups, the ANCOVA model will be implemented within mixed model framework where <repeated/group=> option will be used to allow separate estimation of residual variance between the groups.

Further information on the multiple imputation method is presented in [Appendix 4](#).

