9.2. Administration of Investigational Medicinal Product

Patients will be instructed to ingest, placebo starting at Visit S2 for the duration the placebo run-in period and the IMP starting at Visit T1 for the duration of treatment period orally once daily (once every 24 hours) at approximately the same time each day with water. IMP may be taken with or without food. On clinic visit days, patients will be instructed to delay ingestion of IMP until all study procedures have been completed. If a patient arrives at clinic on Visits T4 or T5 or T7 without having fasted or having taken IMP before arriving at the clinic, reschedule the visit (the next day or as soon as possible) so that the fasting and dosing requirements have been met. Patients will be instructed to return all packaging and unused IMP at each clinic visit.

If the patient forgets to take IMP at the usual time on nonclinic visit days, it may be taken up to 12 hours later the same day. After that time, the patient should not take IMP that day and should resume ingestion of IMP the following day. If a patient fails to take IMP, details describing the reasons for nondosing should be documented in the patient's medical records and eCRF. Extra IMP (7 extra days per bottle) is provided and can be used, if needed, prior to the next visit or to replace a dose of IMP that cannot be used because it is lost or damaged.

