10.3. Subject Withdrawal Criteria

10.3.1. Early Withdrawal from the Study

Patients must remain in the study until the last scheduled visit at Week 52 (Visit T7) to be considered as having completed participation in the study.

Patients who withdraw from IMP prior to Week 52 (Visit T7) for any reason will be asked to continue to be followed for safety assessments, including basic fasting lipids, at clinic visit following the protocol-specified visit schedule (see [Appendix 1](#)).

Patients who temporarily withdraw from IMP prior to Week 52 (Visit T7) for any reason may restart IMP providing that 1) the patient and the investigator are in agreement regarding this course of action, 2) the patient has been off of IMP for 4 weeks or less; and 3) IMP can be started as soon as possible. For cases where the patient has been off of IMP for more than 4 weeks, the investigator must contact the medical monitor for approval prior to restarting IMP.

Patients who refuse to continue to return to the clinic for safety assessments will be asked to participate in phone calls from the site at protocol-specified visits (see [Appendix 1](#)), or at a minimum at 52 weeks, to collect information on AEs, concomitant medications, and current health status. The patient must provide consent to be contacted by phone by site personnel for the purposes of assessing current AEs and current health status.

The patient's decision to participate in the clinical study is voluntary. Patients may refuse to continue in the study and/or withdraw from participation in this study at any time, for any reason, specified or unspecified, and without penalty or loss of benefits to which the patient is otherwise entitled.

It is the right and duty of the Investigator to interrupt the treatment of any patient whose health or well-being may be threatened by continuation in this study. Such patients should be withdrawn from the study and should not be continued under a modified regimen.

Patients who are withdrawn from the study may not re-enter. The reasons for withdrawal from this study may include:

- Patient's withdrawal of consent
- Failure to comply with the protocol
- Lost to follow-up
- Illness, condition, or procedural complication (including AEs) affecting the patient's ability to participate or requiring prohibited medication
- The Sponsor or Investigator terminates the study

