5.2. FULL ANALYSIS SET [FAS]

The Full Analysis Set (FAS), used for all of the efficacy analysis, is defined as all randomized patients. The FAS is also known as the intention-to-treat (ITT) set of patients. Patients in the FAS will be included in their randomized treatment group, regardless of the treatment they actually received.

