6.4. VISIT WINDOWING

Protocol-defined assessments will be “slotted” to study weeks based on collection date and applying the rules summarized in the following table. If there is more than one scheduled visit in a visit window, the visit closest to the target date will be used. If there is a tie between the numbers of days from the target date, the visit after the target date will be used. Unscheduled visits that fall within the protocol-defined visit windows will be summarized in the by-visit analyses if there is no scheduled visit available. If there is more than one unscheduled visit within the protocol-defined visit window and no scheduled visit available, the unscheduled visit closest to the scheduled visit date will be used. If there is a tie between the numbers of days from the target date, the visit after the target date will be used.

However, exposure data obtained from the drug accountability and administration CRF will be summarized and listed according to nominal visit information.

Analysis Visit	S1	S2	S3	T1	T2	T3	T4	T5	T6	T7
Study Week	-5	-4	-1	week 0	4	8	12	24	36	52/EOS
Target Study Day	-35	-28	-7	1	29	57	85	168	252	365
Analysis Visit Windows	$[-\infty, -32]$	$[-31, -18]$	$[-17, -1]$	$[1, 1]$	$[2, 43]$	$[44, 71]$	$[72, 127]$	$[128, 211]$	$[212, 309]$	$[310, \infty]$

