17.2.3.4. Observed Data Analysis

The observed case data with no imputation for missing data will be used in sensitivity analyses for primary and key secondary endpoints to explore any difference between a observed analysis vs. missing data imputation using PMM method.

17.2.4. **SUBGROUP ANALYSIS OF PRIMARY EFFICACY VARIABLE**

The primary endpoint for LDL-C will be analysed within subgroups below using the same analysis method previously described. The treatment and subgroup interaction will be examined by including the interaction term in the ANCOVA model for the overall population first. No imputation will be performed on missing data for subgroup analyses. In case the number of subjects within a subgroup is too small, e.g. less than 5% of the overall population, the analyses may not be performed or the subgroup levels may be combined. Forest plots for the primary efficacy variable will also be presented.

- CV risk category (HeFH (with or without ASCVD) vs. ASCVD only)
- Baseline statin intensity (Low or Moderate, vs. High)
- Baseline LDL category ($<130\text{mg/dL}$, $\geq 130\text{ mg/dL}$ and $< 160\text{ mg/dL}$, $\geq 160\text{mg/dL}$) (efficacy only)
- History of diabetes (yes vs.no)
- Age ($< 65\text{ yrs.}$ vs. $\geq 65\text{ yrs.}$ and $<75\text{ yrs}$ vs. $\geq 75\text{ yrs}$)
- Race (White vs. other)
- Gender (male vs. female)
- Region (North America vs. EU)
- BMI category (< 25 vs. $25 - < 30$ vs. $\geq 30\text{ kg/ m}^2$)

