APPENDIX 2. PARTIAL DATE CONVENTIONS

Imputed dates will NOT be presented in the listings.

Algorithm for Treatment Emergence of Adverse Events:

START DATE	STOP DATE	ACTION
Known	Known	If start date < study med start date, then not TEAE If start date >= study med start date and <=study med end date + 30, then TEAE
	Partial	If start date < study med start date, then not TEAE If start date >= study med start date and <=study med end date + 30, then TEAE
	Missing	If start date < study med start date, then not TEAE If start date >= study med start date and <=study med end date + 30, then TEAE
Partial, but known components show that it cannot be on or after study med start date	Known	Not TEAE
	Partial	Not TEAE
	Missing	Not TEAE
Partial, could be on or after study med start date	Known	If stop date < study med start date, then not TEAE If stop date >= study med start date and <=study med end date + 30, then TEAE
	Partial	Impute stop date as latest possible date (i.e. last day of month if day unknown or 31st December if day and month are unknown), then: If stop date < study med start date, then not TEAE If stop date >= study med start date and <=study med end date + 30, then TEAE
	Missing	Assumed TEAE
Missing	Known	If stop date < study med start date, then not TEAE If stop date >= study med start date and <=study med end date + 30, then TEAE
	Partial	Impute stop date as latest possible date (i.e. last day of month if day unknown or 31st December if day and month are unknown), then: If stop date < study med start date and <=study med end date + 30, then not TEAE

Statistical Analysis Plan

START DATE	STOP DATE	ACTION
		If stop date >= study med start date and <=study med end date + 30, then TEAE
	Missing	Assumed TEAE

Algorithm for Prior / Concomitant Medications:

START DATE	STOP DATE	ACTION
Known	Known	If stop date < study med start date, assign as prior If stop date >= study med start date and start date <= end of treatment, assign as concomitant If stop date >= study med start date and start date > end of treatment, assign as post study
	Partial	Impute stop date as latest possible date (i.e. last day of month if day unknown or 31 st December if day and month are unknown), then: If stop date < study med start date, assign as prior If stop date >= study med start date and start date <= end of treatment, assign as concomitant If stop date >= study med start date and start date > end of treatment, assign as post treatment

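### Does the primary imputation fail for patients who have no Week 12 visit date?

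*SAP*

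**What the plan says.** SAP 17.1.3 uses a pattern mixture model with two branches for patients with missing Week 12 lipids. One test places a patient in the off-treatment branch: "defined by date of last dose of study medication is < Week 12 visit date -7". The reason given for treating this group separately is that its members "can be assumed to no longer be benefitting from study medication"; they are imputed from placebo patients with no treatment term. Those whose last dose falls on or after that cut-off are imputed from their own arm. SAP 17.2.1 applies the method to the key secondary endpoints. Appendix 4 extends it to Week 24 and turns the split into a Yes/No column.

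None of the places where a fallback might sit supplies one:
- SAP 6.4 gives target days (85 for Week 12, 168 for Week 24), but uses them to assign collected assessments "to study weeks based on collection date and applying the rules summarized in the following table".
- SAP Appendix 2 handles partial dates for medications and, under "Algorithm for Treatment Emergence of Adverse Events", for adverse events.
- SAP 7.4 sends the reader to a section 15.1.2 that does not exist, a clerical slip for 17.1.3.

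SAP 5.2 says that the FAS is "used for all of the efficacy analysis, is defined as all randomized patients", so patients without a visit must still be imputed. SAP 17.2.3.4 adds an observed-data analysis "to explore any difference between a observed analysis vs. missing data imputation using PMM method".

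**The concern.** Both branches compare the last dose with a date that a patient lost before Week 12 does not have. Read literally, the rule gives that patient no branch, although the FAS requires one. If the comparison were coded directly in SAS (SAP 6.7), a missing date ranks below any number. The on-treatment condition would then be true, and a dropout would be given the benefit of the arm left behind.

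Either outcome favours bempedoic acid in the primary analysis and carries into the key secondary endpoints. The affected patients are also the clearest examples of those the off-treatment branch was written for. Protocol 10.3.1 allows contact with patients who refuse clinic visits to be as sparse as a call "or at a minimum at 52 weeks, to collect information on AEs, concomitant medications, and current health status", so some patients may well have no Week 12 date of any kind.

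**Working it through.** **The plan's own figure.** SAP 7.1: 500 and 250 patients, SD 15, difference 15, two-sided 5%. SE = 15 × √(1/500 + 1/250) = 1.16, and 15/1.16 = 12.9 SEs. Power exceeds 0.999, which agrees with the stated figure of more than 95%.

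**Where the missing date matters.** A value can be missing at a visit that has a date. Protocol 9.2 covers patients arriving "without having fasted or having taken IMP before arriving at the clinic, reschedule the visit", but Protocol 11.1.6.2 and 11.7.2 say that a sample failing the fasting criterion is not taken, and is drawn later only if the visit can be moved within 3 days. Such a patient has a visit date. By the note to Protocol Appendix 1, patients off drug who keep attending do not give apoB or hs-CRP samples, so those values are also missing at dated visits. The same note schedules phone contacts for those who will not attend, and a Week 12 call could supply a date. What remains is patients with no contact around Week 12.

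**Which branch they belong in.** From SAP 6.4, the Week 12 target gives 85 − 7 = Day 78 and the Week 24 target gives 168 − 7 = Day 161. A patient gone before the Week 12 window opens on Day 72 has a last dose no later than Day 71, which is below 78. One gone before the Week 24 window opens on Day 128 has a last dose no later than Day 127, which is below 161. The protocol window for Week 12 (85 ± 3) would give cut-offs from Day 75 to Day 81, and an early dropout is off treatment under any of them.

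**Size if it went wrong.** The documents give no rate, so all shares are assumed. Let u be the share of the bempedoic acid arm that is off drug with no value and no date, and assume that the effect is lost on stopping. Placebo patients have no effect to lose. Assume also that 2% are missing on drug and 3% are off drug with data. The mean effect among observed patients is O = 15 × [1 − 0.03/(1 − u − 0.02)]. Intended routing gives O × (1 − u) and own-arm routing gives O, so the shift is u × O.

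| u | O (own-arm routing) | Intended | Shift | Shift in SEs |
|---|---|---|---|---|
| 1% | 14.54 | 14.39 | 0.15 | 0.13 |
| 2% | 14.53 | 14.24 | 0.29 | 0.25 |
| 4% | 14.52 | 13.94 | 0.58 | 0.50 |

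A paired simulation (1,500 trials per scenario, regression-mean imputation) gives shifts of 0.148, 0.288 and 0.583. Leaving the patients out agrees with own-arm routing to within 0.001. With the 22-point effect from Protocol 4.2.4 the shifts are 0.21, 0.43 and 0.85. At 10%, share times effect is 0.10 × 15 = 1.5 points. The estimate without that overstatement is 13.5, or 13.5/1.16 = 11.6 SEs, so power stays above 0.999. With no true effect and 8% undated (600 trials), rejection was 4.5% with own-arm routing and 4.0% with the target day.

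**Whether the observed-data analysis would hide it.** Let d be the share off drug with no value but with a date; these go correctly to the placebo-based branch. Misrouted imputation then gives O × (1 − d), against O for observed data, a difference of d × O: about 0.15, 0.29 and 0.58 points at d = 1%, 2% and 4%. The two results coincide only if d = 0.

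**Appendix 4.** Cohort 3 (placebo, off treatment) is imputed in the model with a treatment term and bempedoic acid donors, contrary to 17.1.3. The treatment term already gives these patients the placebo level, and only the strata and baseline coefficients are shared across arms. Moving them to the placebo-only model shifts the mean estimate by at most 0.003 points. Row 4 describes its donors as off treatment although cohort 5 is on treatment. That is a labelling slip; the cohort numbers and the code agree.

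**The case for a change.** The best argument for a change is that the authors knew how to write a fallback and did not write one here: SAP 6.1 replaces a missing first-dose date with the randomization date. Both literal outcomes favour the drug, the analysis is the primary one, and one sentence naming the target day would close the gap. The observed-data analysis does not isolate the problem, because the gap between misrouted and intended results stays at u × O whatever d is.

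The omission, the direction of any error and this limit of the observed-data analysis all stand. The likelihood of harm does not. Own-arm routing is an assumption about programming, and it would place a patient known to have stopped in the group defined as still taking drug. Leaving patients out would show as a count below the number randomized. SAP section 8 says that output templates accompany the SAP, and Appendix 1 expects their programming notes to cover missing values. Those templates are not in the public documents, so a rule's absence there cannot be assumed. Nor does any text support the idea that a missing lipid value usually means a missed visit.

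**Conclusion.** This is a gap that analysts fill sensibly. The text omits a reference date for patients with no Week 12 or Week 24 visit, but the stated intent and the target days in SAP 6.4 lead to one reading: someone who left early is off treatment and is imputed from placebo. If the code followed that reading, writing it down changes no result.

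If it did not, the overstatement would be 0.15 to 0.58 points at an assumed 1% to 4% undated, at most half a planning SE. That supposes complete loss of effect in each such patient, and it grows in proportion to a rate the documents do not give. Significance and Type I error are not at risk under the planning assumptions. The Appendix 4 inconsistencies are clerical in effect. The SAP addendum shows that the study is already unblinded, so stating the rule as programmed belongs to ordinary documentation in the study report and needs no amendment to the plan.
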